1. STUDY SYNOPSIS

Study Title	A Phase I/II, randomized, prospective, controlled, multi-center, open-label, two-arm study evaluating the safety and preliminary efficacy of sFilm-FS in controlling liver bleeding during elective surgery
Study Code	HEM-01-17
EudraCT N.	2018-000434-34
Clinical Phase	Phase I / II
Study Objectives	
The primary objective of this study is to evaluate the safety of sFilm-FS versus an active-comparator (TACHOSIL[®]) when used as adjunct to conventional hemostatic techniques during elective liver surgery.
 
The secondary objective of this study is to preliminarily evaluate the hemostatic efficacy of sFilm-FS in controlling liver bleeding during elective surgery.

Study Design	
This is a randomized, prospective, controlled, multi-center, open-label, two-arms study evaluating the safety and preliminary efficacy of sFilm-FS in controlling liver bleeding during elective surgery.
 
Patients will be randomized with a 1:1 allocation ratio to either sFilm-FS (investigational product) or TACHOSIL[®] (active-comparator). All patients will be followed post-operatively through discharge and up to 6 months post-surgery, following the Schedule of Assessments provided below.
 
A Data Safety Monitoring Board (DSMB) will be established and have responsibility for the review of data and identification of any potential safety issues throughout the study. If necessary, the DSMB will make recommendations regarding protocol revisions and will recommend whether the study should proceed based on the safety data considering established stopping rules.

Study Procedure	
The surgical procedure will be performed as per standard of care at the investigational site. A target bleeding site (TBS) will be identified intra-operatively by the Investigator when liver bleeding is encountered during surgery and conventional methods of bleeding control are ineffective.
 
Target Bleeding Site (TBS) is defined as the first bleeding site in which conventional methods of bleeding control (i.e., suture, ligature, cautery) are ineffective or impractical. The TBS must be a site where occlusion of the injured surface blood vessels is required to achieve hemostasis. It must be possible to cover the TBS adequately, with an appropriate overlap, using a single unit of product (sFilm-FS or TACHOSIL[®]). This excludes bleeding from large defects in large arteries or veins requiring repair.
 
Once the TBS has been identified, the Investigator will immediately enroll and randomize the patient into one of the following treatment arms, according to a pre-determined randomization scheme:

	
 • Group A (investigational product): sFilm-FS will be applied at the target bleeding site immediately after conventional methods of control have been exhausted. The sFilm-FS should cover adequately the entire TBS. Following application of sFilm-FS, the Investigator will immediately apply manual compression continuously for at least 2 minutes. A surgical sponge may be used to assist in providing adequate pressure. Hemostasis will be assessed after carefully releasing the compression at the site. sFilm-FS should not be removed once bleeding has stopped. A maximum of 4 units of sFilm-FS may be used per patient. • Group B (active comparator): TACHOSIL® will be applied at the target bleeding site immediately after conventional methods of control have been exhausted. TACHOSIL® should be applied as per the approved prescribing information, with manual compression for at least 3 minutes. A maximum of 4 units of TACHOSIL® may be used per patient. 
If additional bleeding sites/regions requiring a topical hemostatic product are identified after the treatment of the initial target bleeding site, these bleeding sites should be treated with the same study treatment according to the patient's randomization assignment, if clinically appropriate. These areas will not be assessed for hemostasis, but information will be recorded.

Investigational Product	sFilm-FS is a sterile bio-compatible bio-absorbable patch which consists of a polymeric film composed of a tri-block polymer (device component) containing Polyethylene Glycol (PEG) Poly-Caprolactone (PCL) and Poly-Lactide Acid (PLA), embedded with lyophilized powders of Human Fibrinogen, Human Thrombin (biological components) and calcium chloride. sFilm-FS is supplied ready to use in the patch size of 5 x 5 cm (~ 2 x 2 inch).
Comparator Product	TACHOSIL® is a fibrin sealant patch composed of an equine collagen patch coated with Human Fibrinogen and Human Thrombin. The product is ready for use and for the study it will be supplied in patch size of 4.8 x 4.8 cm (1.9 x 1.9 inch).
Study Population	Patients undergoing elective, open abdominal surgery in which liver bleeding is expected, with presence of an appropriate target bleeding site (TBS) identified intra-operatively by the Investigator. 30 completed patients are to be enrolled in this study.

Inclusion Criteria	
 1. Patients (males or females) aged \geq 18 years old. 2. Patients requiring elective surgery in which liver bleeding will be encountered. 3. Hemoglobin \geq 8.0 g/dL within 24 hours prior to surgical procedure. 4. Patients understanding the nature of the study and providing their informed consent prior to participation. 5. Patients willing to participate in the study and able to attend the visits and procedures foreseen by study protocol. 
Intra-operative inclusion criteria:
 
 6. Patients with a target bleeding site (TBS) identified by the Investigator during surgery in which liver bleeding will be encountered.
Exclusion Criteria	
 1. Patients having undergone a therapeutic surgical procedure within 30 days from the study enrolment. 2. Patients with a severe coagulopathy defined as INR $>$ 2.0. 3. Patients with platelet count $<$ 50,000 x10⁹ PLT/L at the screening (ref. 11). 4. Patients admitted to trauma surgery. 5. Transplant patients due to fulminant hepatic failure. 6. Patients with known or suspected allergy or hypersensitivity to blood products or to one of the components of sFilm-FS or the active-comparator. 7. Patients with anesthesia risk judged to be higher than ASA3 by the Investigator. 8. Patients with at least one of the following concomitant conditions: severe co-morbid conditions known to pose a high risk for surgery and adequate recovery (i.e., liver cirrhosis with Child-Pugh score B or C, cholestasis, heart diseases), immunodeficiency diseases, blood clotting disorders, any conditions known to effect wound healing (i.e., collagen vascular disease), known or current alcohol or drug abusers. 9. Patients suffering from claustrophobia. 10. Patients with implanted or embedded metal objects, prostheses, pacemaker, or fragments in the head or body that would present a risk during the MRI scanning procedure or have worked with ferrous metals either as a vocation or hobby or following trauma (i.e., sheet metal workers, welders, or machinists) in such a way that might have led to unknown, indwelling metal fragments that could cause injury if they moved in response to placement in the magnetic field. 11. Patients being treated with at least one of the following treatments: antibiotic therapy for active infection, fibrin sealants, systemic steroids, or immunosuppressive agents. 12. Patients who are participating or have participated in other clinical studies within the 30 days before the study enrolment. 13. Female patients who are pregnant or breast-feeding or who wish to become pregnant during the period of the clinical study and for three months later. 14. Female patients of childbearing age (less than 24 months after the last menstrual cycle) who do not use adequate contraception. *

	
Intra-operative exclusion criteria:
 
15. Patients identified with a TBS with major arterial bleeding requiring suture or mechanical ligation.
 
16. Patients identified by the Investigator to have intra-operative bleeding from large defects in large arteries or veins, requiring repair.
 
17. Patients identified by the Investigator to have intra-operative findings that may preclude conduct of study procedure.
 
18. Patients having an active local infection in the anatomic surgical area.
 
19. Patients with occurrence of major intra-operative complications that require resuscitation or deviation from the planned surgical procedure.
 
20. Patients with bleeding site in or near to foramina in bone.
 
* Adequate contraceptive methods may include any approved method of birth control such as combined estrogen and progestogen containing hormonal contraception, associated with inhibition of ovulation (oral, intravaginal, transdermal), progestogen-only hormonal contraception associated with inhibition of ovulation (oral, injectable, implantable), intra-uterine devices, condoms, abstinence or vasectomized partner. Contraception should be maintained until study end.

Primary Endpoint	
The primary endpoint of the study is the evaluation of safety. Safety will be assessed from randomization of patients until the last follow-up visit and will include evaluation of treatment emergent adverse events. In particular, patients will be followed for AEs related to bleeding at TBS, thrombotic events, transfusion-related complications, post-operative adhesions (MRI assessment) as well as vital signs, physical examination, urine analysis, blood / coagulation parameters profiles, antibodies against fibrinogen and thrombin, and signs of systemic inflammation.

Secondary Endpoints	
The secondary endpoints of the study are related to product hemostatic efficacy. For this purpose, hemostasis and treatment failure are defined.
 
Hemostasis is defined as an absence/cessation of bleeding at the target bleeding site (TBS) according to the surgeon's judgement, so that the surgical closure of the field could be started.
 
Treatment failure is defined as follows:
 
 - in case the bleeding at TBS (or re-bleeding) is still observed after 10 minutes following first application of study product; - if hemostasis at TBS is achieved, but the Investigator decides that an additional treatment is required to ensure the durability of hemostasis; - if there is a breakthrough bleeding requiring treatment other than the study product, at any time

Secondary Endpoints	
Secondary endpoints include:
 
 • Proportion of patients achieving hemostasis at TBS at 2 (applicable only for sFilm-FS), 3, 5, 7 or 10 minutes following first product application, without the occurrence of re-bleeding, starting from 10 minutes from first product application and until the completion of surgical closure. • Incidence of re-treatment (one or more additional patch of sFilm-FS or TACHOSIL®) at the TBS at the different time points (2 for sFilm-FS, 3, 5, 7, 10 minutes from first product application). • Time to Hemostasis from first product application (TTHP). Time to Hemostasis from patient randomization (TTHR) will be collected as well but will not be used as endpoint. • Percentage of total patients (patients that achieved hemostasis with a single patch application and patients that required additional patches) that have achieved hemostasis 10 minutes after first product application and therefore did not need to convert to standard of care treatment at the end of these 10 minutes. • Incidence of treatment failure based on pre-defined treatment failure criteria (see definition in Section 11.1.3 of the protocol). • Incidence of transfusion requirements in the 6 months follow up period.
Sample Size	
The sample size will be of 30 patients completing the study. 15 patients will be included in the experimental treatment arm (Group A) and 15 patients in the active-comparator arm (Group B) to allow an adequate comparison between treatments. Dropped patients during the course of the study will be replaced.

Statistical Analysis	
Data will be summarized with respect to demographic and baseline characteristics, efficacy and safety measurements. The statistical analysis will be performed on:
 
 • Patients' disposition; • Background and baseline characteristics; • Concomitant therapies; • Safety: 
 ◦ adverse events ◦ vital signs ◦ physical examinations ◦ MRI assessment ◦ laboratory tests (including testing for antibodies) • Efficacy: 
 ◦ hemostasis ◦ treatment failure ◦ re-treatment ◦ time to hemostasis

	
Data will be summarized separately by treatment arm. Safety and efficacy analyses will be descriptive. Proportions of patients achieving hemostasis, experiencing treatment failure, and needing re-treatment will each be estimated along with 95% exact confidence intervals (CIs). Median time to hemostasis from first product application will be estimated using Kaplan-Meier methods.

--	---

2. **SCHEDULE OF ASSESSMENTS**

Visit Type	Screening	Baseline	Surgery	Post-Surgery to Hospital Discharge (HD)	Hospital Discharge (HD)	Follow-Up #1	Follow-Up #2	Follow-Up #3	Follow-Up #4
Visit N.**	1	2*	3	4	5	6	7	8	9
Study Day	D-21 to D-1	D-1	D0	Daily from D1 to D-HD	D-HD	D30 (±3)	D60 (±7)	D120 (±14)	D180 (±14)
Informed Consent collection	X								
Inclusion/Exclusion Criteria evaluation	X	X	X						
Demographics/Medical History	X								
Physical Examination	X	X			X	X	X	X	X
Vital signs ¹	X	X	X	X ¹¹	X	X	X	X	X
Pregnancy test ²	X	X							
Blood hematology & biochemistry ³	X	X	X	X ¹¹	X	X	X	X	X
Urine analysis ⁴	X	X	X		X	X			X
Coagulation (PT, PTT, INR)	X	X	X		X	X			X
Serum sample collection ⁵	X								
Antibodies testing ⁶	X					X			X
MRI assessment ⁷	X								X
Randomization				X					
Product application				X					
Operative/Surgical information collection ⁸				X					
Intra-operative details collection ⁹				X					
Determination of hemostasis at TBS ¹⁰				X					
Use of other hemostatic measures				X					
Adverse Events				X	X	X	X	X	X
Transfusion requirements				X	X	X	X	X	X
Bleeding, thrombotic, and transfusion-related complications				X	X	X	X	X	X
Concomitant medications	X	X	X	X	X	X	X	X	X

- * V2 to be skipped in case V1 is performed one day before surgery (D-1).
- ** All patients can request or be requested to be evaluated in an additional visit (i.e., in case of suspected adverse events).
- 1 Vital signs will include blood pressure, heart rate, temperature, and respiratory rate.
- 2 β -HCG urine pregnancy tests will be conducted in case of patients with childbearing potential.
- 3 Blood hematology and biochemistry tests include: Hb, HC, MCH, MCHC, MCV, RBC, WBC, PLT, Fibrinogen, lactate, D-Dimer, AT, ESR, CRP, BUN, creatinine, uric acid, BIL, LDH, AST (SGOT), ALT (SGPT), Gamma-GT, Na, Ca, P, glucose, albumin, total protein.
- 4 Urine analysis tests include: specific gravity, pH, glucose, protein, blood, ketones, microscopic examination.
- 5 A serum sample will be collected and stored at -70°C for possible future viral safety testing.
- 6 Measurement of levels of antibodies against Human Fibrinogen and Human Thrombin. For this purpose, a serum sample will be collected and stored at -70°C for testing at the end of the study.
- 7 Additional MRI will be performed throughout the study if the investigator identifies signs and symptoms of unanticipated or unexpected persistent inflammatory response, or unexplained abdominal pain or other symptoms (for instance signs of adhesions, bowel obstruction, etc.).
- 8 Operative/surgical information include OR time, procedure time, time from liver resection/incision to initiation of fascial closure, drain usage, estimated blood loss, cell salvage use, transfusion information (if applicable), length of stay (ICU and overall LOS).
- 9 Intra-operative details include hepatic parenchyma classification type (normal or abnormal, steatotic, cirrhotic or other), Investigator description of the TBS (area, density, arterial/venous/mixed, intensity of flow), alternative methods used to achieve hemostasis (if applicable), estimated TBS treated area and total resected area, number of product units applied at the TBS and at other areas rather than the TBS, incidence of post-operative bile leaks requiring intervention, hepatic segment information (anatomic resection/non-anatomic resection).
- 10 Patients will be monitored for absence of bleeding at 2, 3, 5, 7, and 10 minutes after product application and thereafter, before closing the site.
- 11 Assessments to be taken daily from one day after surgery (D1) until hospital discharge (D-HD).

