7.3.2. Stopping Rules

If one of the following occurs during the enrollment period of patients receiving the test article (sFilm-FS) the study will be immediately suspended:

- Three or more patients developed a suspected unexpected serious adverse reaction (SUSAR) caused by a TBS post-operative re-bleeding (not requiring surgery re-intervention);
- Two or more patients had a TBS re-bleeding events following final observation period that required surgery re-intervention;
- Three or more patients developed other possible serious adverse reactions like thromboembolic events or severe allergic reactions.
- Three or more patients develop serious unanticipated or unexpected local reactions (serious adverse events) such as:
 - Signs of local reactions affecting the spleen and liver (persistent pain in the area of the application that is unanticipated or unexpected)
 - Persistent unanticipated and unexpected Systemic inflammatory response syndrome (SIRS), defined with at least two of these conditions: body temperature over 38 or under 36 degrees Celsius, heart rate greater than 90 beats/minute or respiratory rate greater than 20 breaths/minute or partial pressure of CO₂ less than

- 32 mmHg, leucocyte count greater than 12000 or less than 4000 /microliters or over 10% immature forms or bands
- Reactions on other local organs such as adhesions and reactions impacting the intestinal tract etc., assessed as being due to local reactivity. This would be diagnosed as a bowel obstruction that is unanticipated.

These stopping rules only apply to the investigational treatment group (Group A). The active-comparator group (Group B) patients should be followed according to the Investigator's standard practice as clinically appropriate.

After study suspension, the Data Safety Monitoring Board (DSMB), together with the Sponsor, will review the data and decide whether to continue or terminate the study.

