8. STUDY POPULATION

8.1. Patient Screening Procedures

All patients requiring surgery in which liver bleeding will be encountered will be screened by each center for study inclusion. For each patient screened, all data will be registered in the eCRF, including the reason/s for exclusion for patients who are ineligible for enrollment.

Final enrollment of patients will be based on meeting all criteria, including intra-operative criteria observed at day of surgery (Day 0).

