8.3. Exclusion Criteria

1. Patients having undergone a therapeutic surgical procedure within 30 days from the study enrolment.
2. Patients with a severe coagulopathy defined as INR $>$ 2.0.
3. Patients with platelet count $<$ 50,000 $\times 10^9$ PLT/L at the screening (ref. 11).
4. Patients admitted to trauma surgery.
5. Transplant patients due to fulminant hepatic failure.
6. Patients with known or suspected allergy or hypersensitivity to blood products or to one of the components of sFilm-FS or the active-comparator.
7. Patients with anesthesia risk judged to be higher than ASA3 by the Investigator.
8. Patients with at least one of the following concomitant conditions: severe co-morbid conditions known to pose a high risk for surgery and adequate recovery (i.e., liver cirrhosis Child-Pugh with score B or C, cholestasis, heart diseases), immunodeficiency diseases, blood clotting disorders, any conditions known to effect wound healing (i.e., collagen vascular disease), known or current alcohol or drug abusers.
9. Patients suffering from claustrophobia.
10. Patients with implanted or embedded metal objects, prostheses, pacemaker, or fragments in the head or body that would present a risk during the MRI scanning procedure or have worked with ferrous metals either as a vocation or hobby or following trauma (i.e., sheet metal workers, welders, or machinists) in such a way that might have led to unknown, indwelling metal fragments that could cause injury if they moved in response to placement in the magnetic field.
11. Patients being treated with at least one of the following treatments: antibiotic therapy for active infection, fibrin sealants, systemic steroids, or immunosuppressive agents.
12. Patients who are participating or have participated in other clinical studies within the 30 days before the study enrolment.
13. Female patients who are pregnant or breast-feeding or who wish to become pregnant during

the period of the clinical study and for three months later.

14. Female patients of childbearing age (less than 24 months after the last menstrual cycle) who do not use adequate contraception.*

Intra-operative exclusion criteria:

15. Patients with a TBS identified with major arterial bleeding requiring suture or mechanical ligation.
16. Patients identified by the Investigator to have intra-operative bleeding from large defects in large arteries or veins, requiring repair.

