14.2 Study Population

The Intention-To-Treat (ITT) population will include all Patients registered, who underwent surgery and received the dose of study treatment and, with no major violations of the eligibility criteria. This population is considered as primary and will be used for all efficacy analyses.

The safety population will include all patients registered, who received one dose of study treatment. This population will be used for safety analysis.

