4 STATISTICAL ANALYSIS SETS

4.1 Definition of Sets for Statistical Analysis

Safety Analysis Set (SAF)
The Safety Analysis Set will consist of all patients who received at least one dose of any study medication.
Full-Analysis Set (FAS1)
FAS is defined as all randomized patients who underwent surgery, received at least one dose of study treatment and having no major violations of inclusion and exclusion criteria. Patients will be analyzed according to the treatment randomized regardless of which treatment was actually received.
Full-Analysis Set (FAS2)
FAS2 is an extension of the FAS1 and is defined as all randomized patients who underwent surgery, received at least one dose of study treatment.
Per-protocol set (PPS)
All patients according to the FAS definition without important/ major protocol deviations as specified in sec. 4.2.

For application of the different analysis sets to the analyses to be performed see sec. 6.3.

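### The platelet exclusion threshold combines a number and a unit that cannot both be right; read literally, it excludes every patient

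*Protocol*

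**What the plan says.** Exclusion criterion 3 in the protocol synopsis sets the lower platelet limit at "50,000 x10⁹ PLT/L at the screening". Section 8.3 repeats the same number and unit. Both copies cite reference 11 as support. Neither the protocol nor the SAP gives another platelet threshold or a correction of the unit. For eligibility, SAP section 3.1 simply refers back to protocol sections 8.2 and 8.3.

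The criterion is binding. Protocol section 8.1 states: "Final enrollment of patients will be based on meeting all criteria". Eligibility also carries through to the analysis. The ITT population in protocol section 14.2, which is primary for efficacy, is restricted to patients "with no major violations of the eligibility criteria". In SAP section 4.1, FAS1 is restricted to patients "having no major violations of inclusion and exclusion criteria", and the per-protocol set takes the FAS definition and also removes patients with major deviations.

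**The concern.** A threshold of 50,000 would be on a familiar scale if it were a count per microlitre. Attached to x10⁹ per litre, it describes a concentration that no patient could reach. Because the criterion excludes patients below the limit, the error works in the worst direction: it does not make the rule lax, it makes everyone ineligible.

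Three things depend on this line:

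- **Enrolment.** A site cannot follow the criterion as written. Each centre must substitute its own reading, and the protocol offers nothing to check that reading against. SAP section 3.5 lists three centres, and under protocol section 11.2 platelet counts come from local hospital laboratories.
- **Data checks.** Protocol section 18.1 describes predefined computerised consistency checks. If one was programmed from this text, it would flag every patient.
- **Analysis sets.** If those flags were graded as major violations, the ITT population, FAS1 and the per-protocol set would lose patients for a reason that is purely notational. With 15 patients per arm, even one misclassification would matter.

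**Working it through.** **Inputs**

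- Threshold as stated (synopsis, criterion 3; section 8.3, criterion 3): platelets < 50,000 x 10⁹/L.
- Conversion: 1 L = 10⁶ microlitres.
- Comparison within the protocol: the stopping rules in section 7.3.2 give another blood cell count as an unscaled number per microlitre, "leucocyte count greater than 12000 or less than 4000 /microliters".
- The documents give no derivation of the platelet threshold and no platelet reference range. There is therefore no calculation of the plan's own to reproduce, and a range of counts has to be assumed.

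**Step 1: the threshold as written**

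50,000 x 10⁹/L = 5 x 10¹³/L

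5 x 10¹³/L ÷ 10⁶ microlitres/L = 5 x 10⁷ per microlitre = 50,000,000 per microlitre

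**Step 2: would any patient pass?**

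Assume counts from 10 to 5,000 x 10⁹/L, chosen to be far wider than any plausible patient value.

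| Count (x 10⁹/L) | Below 50,000 x 10⁹/L? | Threshold ÷ count |
|---|---|---|
| 10 | yes, excluded | 5,000 |
| 150 | yes, excluded | 333 |
| 450 | yes, excluded | 111 |
| 1,000 | yes, excluded | 50 |
| 5,000 | yes, excluded | 10 |

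Every count in the range meets the exclusion. Even at the upper end of this deliberately extreme range, the threshold is still 10 times too high for anyone to pass.

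**Step 3: the size of the mismatch between scales**

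If the number 50,000 had been meant as a count per microlitre:

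50,000 x 10⁶ = 5 x 10¹⁰/L = 50 x 10⁹/L

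(5 x 10¹³) ÷ (5 x 10¹⁰) = 1,000

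The written figure would then be exactly 1,000 times too large. The per-microlitre leucocyte counts in section 7.3.2 make this explanation plausible but do not prove it. Step 2 does not depend on it.

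**Step 4: could it be a text-extraction error?**

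The synopsis and section 8.3 carry the expression in different typesetting but with the same number, the same power of ten and the same unit. Two independent corruptions giving the same result are unlikely.

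**The case against.** The strongest reply is that nobody would apply the criterion literally. The SAP describes randomisation largely in the past tense and cites a sponsor memo of April 2022, which indicates that patients were enrolled despite the wording. Sites evidently read through it. This stands: the practical effect is a rule that cannot be followed or audited as written, not an empty trial.

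The effect on the analysis sets is also conditional. Under SAP section 4.2, deviations are graded major or minor by the study team with the sponsor and discussed case by case before database lock, so a flag raised on every patient would have to survive that review. The eCRF and the validation plan are not among the documents, so nothing shows that a faulty check exists. The Safety Set, which serves the primary endpoint, and FAS2 have no eligibility filter. SAP section 9.1 reports efficacy on FAS1, FAS2 and the per-protocol set without ranking them. Even in the worst case, the primary analysis and one full set of efficacy results would remain intact. All of this stands, and it limits the weight of the point.

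Finally, the factor of 1,000 rests on an inference about what was meant. That is correct, and it is treated as conditional here.

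None of these arguments makes the text right. To say that everyone knows what was meant concedes that the approved criterion is not the one being used. The exclusions for INR above 2.0 and for clotting disorders do not replace a platelet limit in a study of bleeding control.

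**Conclusion.** The criterion is wrong as written, in both places. Read literally, it excludes 100% of patients. That conclusion rests only on the unit conversion and on the assumption that no patient's count exceeds 5,000 x 10⁹/L. The factor of 1,000 is the gap between the two scales that appear to have been mixed, and it holds if 50,000 was a per-microlitre count; the documents do not confirm this.

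The error does not touch the sample size, the confidence intervals or the safety analysis. Its reach is the documented basis for eligibility and, through the grading of violations, membership of the ITT population, FAS1 and the per-protocol set. It should be corrected, but it does not threaten the main conclusions of the study.

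**What to change.** Restate criterion 3 in the synopsis and in section 8.3 with a number and a unit on the same scale, either per microlitre or x 10⁹/L. The sponsor must confirm the intended figure; none is proposed here. Then check that any eCRF edit check and the eligibility-violation listing use the confirmed figure.

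If enrolment has closed and no further amendment is planned, record the clarification at the data review meeting described in SAP section 5.2, before the SAP is finalised and the database locked. The record should state which threshold the sites actually applied, and every enrolled patient's screening platelet count should be checked against the confirmed figure.

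The cost is one line in two places and a short check of up to about 30 patients' screening values. No analysis changes, and the correction has no downside.
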